1.0 PURPOSE

1.1 Name and Intended Use

The device used in this study is called the SoftWave device.

The intended use of the SoftWave device used in this study is to assess the usability and tissue response to shock wave treatment and to support additional marketing claims.

1.2 Objectives

1. Primary Objective:
 - Collection of Treatment Discomfort/Pain Evaluation
2. Additional Objectives:
 - Evaluation of tissue response through Biopsies at multiple timepoints up to 30 days post treatment (optional):
 - Sample staining as appropriate, such as H&E
 - Nano-string for Gene Expression
 - Device comparison treatment with similar low-intensity shockwave device (optional).
 - Photographic evaluation with Vivosight imaging at the 30 and/or 90 day follow up compared to baseline (optional).
 - Photographic evaluation with 2D and/or 3D imaging at the 30 and/or 90 day follow up compared to baseline (optional).
 - Subject treatment assessment through questionnaires (optional):
 - Subject treatment experience questionnaire
 - Subject follow up questionnaire
 - Subject satisfaction questionnaire
 - Clinician treatment assessment through questionnaires (optional):
 - Clinician treatment questionnaire
 - Clinician satisfaction questionnaire
3. Safety Objectives:
 - Collection of Adverse Events

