2.0 PROTOCOL

2.1 Protocol Methodology and Analysis

Methodology:

Subjects are to be enrolled in this clinical study if they are a healthy male or female 18 – 65 years of age. Up to 50 subjects will be enrolled at 2 study centers. Subjects will attend a screening/pretreatment visit which may be performed on the same day as the treatment visit. Subjects may receive up to 5 treatments with the study device. Subjects may also receive treatment

with a similar shockwave device. Subjects may be consented to have biopsies collected at a specific time after their final treatment, which will occur up to 30 days post treatment. Follow up visits may occur 30 and 90 days post last treatment visit. An unscheduled visit or phone call may be performed at any time during the study at the request of the subject or as deemed necessary by the site Investigator.

Analysis:

Upcoming generations are proving to have an interest in non-ablative aesthetic treatments and will drive demand for innovated products, procedures, and practice design.¹ Due to this shift in patient base, practices need to evolve to adapt to the newer generational ideologies. This device will be using the SoftWave device to collect additional data and imaging. Although this device is cleared for use by the U.S. Food and Drug Administration, there is a need to collect additional data, images, and tissue response to expand marketing claims.

Relevance:

There is an increasing demand for new methods and additional cleared indications for non-invasive treatments using shockwave therapy. Another device currently on the market cleared for use is, but are not limited to, the dermaPACE® System.

Testability:

The SoftWave device, had been previously cleared for the activation of connective tissue (FDA 510(k) K182682), the treatment of chronic, full thickness diabetic foot ulcers (FDA 510(k) K191961), and the treatment of superficial partial thickness second degree burns in adults (FDA 510(k) K200926). This study will utilize the collection of data and imaging to support additional marketing claims.

Compatibility:

Although shock wave technology is a well-known and widely use technique for non-invasive treatments, there is still a need to collect additional data and images, and expand marketing claims and device use.

Predictive power:

Assuming there is an acceptable side effect profile, it would be appropriate to expect results for other marketable indications.

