2.2 Protocol Study Design

This is a prospective, open label, multi-center clinical study to collect additional data and imaging for the SoftWave device.

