2.3 Subject Selection Criteria

Subjects will meet the criteria described below:

Inclusion Criteria:

- A healthy male or female 18 – 65 years of age.
- Willing to undergo treatments with the SoftWave device.

- Understands and accepts obligation not to receive any other procedures on the treatment area through the length of the study.
- Understands and accepts the obligation and is logically able to be present for all visits.
- Is willing to comply with all requirements of the study and sign the informed consent document.

Exclusion Criteria:

- Is pregnant or of childbearing potential and not using medically effective birth control, or has been pregnant in the last 3 months, currently breast feeding or planning a pregnancy during the study.
- The subject has a pacemaker or implantable defibrillator.
- The subject has a severe coagulation disorder.
- The subject has open epiphyseal plates.
- The subject has recently had a steroid injection.
- The subject is currently enrolled in an investigational drug or device trial, or has received an investigational drug or been treated with an investigational device within in the area to be treated 6 months to entering this study.
- The subject has any condition or is in a situation which, in the Investigator's opinion, may put the subject at significant risk, may confound study results or may interfere significantly with the subject's participation.

Be sure to list all concomitant medications taken or procedures performed before, during and after the trial.

Subjects will be recruited for the study through the existing patient database and may use advertisements.

Subject populations will not be eligible to participate in the study if they are vulnerable populations such as children, pregnant women, prisoners, institutionalized individuals, and any persons requiring a legally authorized representative as part of the consenting process.

Subject population characteristics that will not be eligible to participate in the study include non-English speaking individuals and people who cannot read or comprehend English. Employees of the Investigator will be participating in the study.

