2.7 Treatment Procedures

- Procedures for the shock wave treatment:
 - The defined study area will be identified and will be cleansed thoroughly using a facial cleanser or mild soap and water. The treatment area may be marked with a marker.
 - The device may be used in accordance with the Protocol Manual and Instructions for Use.
 - Test spots may be performed prior to treatment in an area, such as on the hand, or in or close to the treatment area or so the subject can get used to the sensation.
 - Ultrasound gel will be applied to the area to be treated.
 - The applicator will be placed on the skin and slowly moved over the identified treatment area administering pulses of acoustic pressure shockwaves.
 - Parameters may be adjusted throughout the treatment to increase subject comfort.
 - Subjects will be asked to report the general level of treatment discomfort/pain on a scale of 0 (none) to 10 (maximum intolerable pain).
 - Parameters and tissue response will be continuously monitored and recorded during treatment.
- The additional treatments will follow the same procedure.
- Subjects and Clinicians may be asked to complete treatment questionnaires.
- Subjects may receive up to 5 treatments. Treatments will be performed every 3 – 14 days.

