2.15.3 Patient Populations

Interim results may be collected and reported. All data will be analyzed at the end of the study on a per device basis as well as overall. The primary analysis will be performed by the intention-to-treat approach. Everyone who begins the treatment is part of the study whether he or she completes the study or not. Additional per-protocol analysis may also be performed on subjects who complete the entire clinical trial according to the protocol. The most appropriate method of handling missing values will be chosen based on the individual trial goals, endpoints and context.

The analysis of demographic, medical history, and efficacy variables will be based on all patients who are randomized and receive at least one treatment. The analysis of safety data will be based on all patients who are randomized, receive at least one treatment, and have at least some safety data.

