2.15.4 Analysis of Demographic and Medical History Variables

Summaries will be prepared for all important demographic and medical history variables. For quantitative variables summaries will include the sample size, mean, median, standard deviation, minimum, and maximum. For these variables the treatment groups will be compared using either a t-test or a Wilcoxon Rank Sum test, as appropriate. For categorical variables the summaries will include the sample size and the number and percent of patients for each outcome. For these variables the treatment groups will be compared using Fisher's Exact test. Statistical significance will be declared if the two-sided p-value is < 0.05.

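### A subject may receive both devices with no rule on area, side, order or allocation, so some per-device results cannot be assigned to one device and per-device pain differences are open to order and selection bias

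*Combined protocol and SAP*

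**What the plan says.** Section 1.2 gives "Device comparison treatment with similar low-intensity shockwave device (optional" as an additional objective, with no endpoint or contrast attached. Section 2.1 states "Subjects may receive up to 5 treatments with the study device" and then, for the similar device, "Subjects may also receive treatment". Section 4.0 names that device as the Eclipse Evive.

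Section 2.2 describes the design: "This is a prospective, open label, multi-center clinical study to collect additional data and imaging for the SoftWave device". Section 2.7 refers to a single area: "The defined study area will be identified and will be cleansed thoroughly using a facial cleanser or mild soap and water". It sets 3 to 14 days between treatments. The visit schedule in section 2.13 has no row or visit for the comparator.

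Section 2.15.3 says "All data will be analyzed at the end of the study on a per device basis as well as overall", and defines its analysis sets by patients who are randomized. Sections 2.15.4 and 2.15.6 refer to treatment groups. For demographic and medical history variables only, "For these variables the treatment groups will be compared using either a t-test or a Wilcoxon Rank Sum test, as appropriate". Section 2.15.6 plans no statistical comparison of pain or adverse events.

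Section 2.3 requires that each subject "Understands and accepts obligation not to receive any other procedures on the treatment area through the length of the study". It does not mention the comparator.

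**The concern.** The word also in section 2.1 puts one person under both devices. A per-device table then needs each observation to belong to one device, and a fair comparison needs the choice of device, side and order to be unrelated to the outcome. The protocol secures neither. By default the site chooses.

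Two things are at stake. First, follow-up outcomes of dual-device subjects would be reported under a device that did not alone produce them, including the optional 80% targets for satisfaction and image identification in section 2.15.1 if these are shown by device. Second, a difference in mean pain between devices could reflect which came first, or who was chosen for the comparator. The data are meant to support marketing claims (sections 1.1 and 2.1), so descriptive per-device tables matter even without a test. Area and order that were not recorded or balanced at the time cannot be recovered by analysis.

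**Working it through.** **1. Search for a rule.** The documents give no area, side, order, gap between devices, number of comparator treatments or assignment method for the comparator. The only side rule is in section 2.10, where a control biopsy comes from the contralateral side. Whether that side stays free of the comparator is not stated. Randomized patients and treatment groups appear only in section 2.15, and no procedure creates either. The relatedness definitions in section 14.0 are framed for the SoftWave treatments only.

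**2. Timing.** Five treatments have four intervals, so a course lasts 4 × 3 = 12 to 4 × 14 = 56 days. Biopsies run to 30 days after the last treatment; follow-up photographs and satisfaction are taken at 30 and 90 days. If the comparator falls within the same course, both devices precede these outcomes.

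**3. Attribution in a dual-device subject.**

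| Outcome | Separate areas | Same area |
|---|---|---|
| Satisfaction, 30/90 days (rated per subject) | Not attributable | Not attributable |
| Follow-up photographs and biopsies | Attributable if area is recorded | Not attributable once both devices have been used |
| Late local adverse events, such as bruising | Attributable if area is recorded | Not attributable |
| Pain at each treatment | Can be labelled; order and selection bias remain | Same |
| Events during a treatment | Attributable to the device in use | Same |

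**4. Share of data affected.** Let k subjects receive both devices. Assume all 50 receive SoftWave and, following section 2.1, that every comparator user also does.
- SoftWave follow-up data from dual-device subjects: k/50. For k = 10 this is 10/50 = 20%; for k = 25 it is 25/50 = 50%.
- Comparator follow-up data from dual-device subjects: k/k = 100%.

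The documents do not give k; these values are illustrations.

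**5. Order bias in pain.** Section 2.7 allows test spots so that subjects become accustomed to the sensation, so an order effect is plausible; its size is not given. Let h be an assumed fall in score from the first device to the second, p the share of dual-device subjects given SoftWave first, and the true device difference zero. Within subject, the bias in SoftWave minus comparator is p·h − (1 − p)·h = (2p − 1)·h. For h = 1 point:

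| p | 1 | 0.75 | 0.5 | 0.25 | 0 |
|---|---|---|---|---|---|
| Bias (points) | +1 | +0.5 | 0 | −0.5 | −1 |

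If instead the mean of all 50 SoftWave subjects is set against the mean of the k comparator subjects, the bias is p·h − (1 − p)·h·k/50. With p = 0.5, h = 1 and k = 25 it is 0.5 − 0.5 × 25/50 = +0.25 point. Balanced order therefore cancels only in the within-subject contrast. Selection of who gets the comparator would add to this by an unknown amount.

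**The case against.** The strongest defence is that the comparison is optional, has no success criterion in section 2.15.1, and involves no test of pain or adverse events. Section 2.3 can also be read as barring a second device on the treated area, and the wording of section 2.15 suggests separate groups may have been intended. All of this is fair. It does not settle the matter: section 2.15.3 asks for per-device results without exception, section 2.3 is silent on the comparator, and separate groups conflict with section 2.1. The manual and instructions for use listed as attachments are not among the supplied documents, but allocation and analysis rules belong in the protocol.

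A reader might infer more than the documents support:
- *That carry-over is certain.* Local carry-over needs both devices on one area, which no section states.
- *That the comparison objective is unanswerable.* Pain is scored at each treatment and can be labelled by device. Outcomes on separate, recorded areas can be attributed.
- *That all outcomes are timed from the last treatment.* Adverse events are recorded from the first treatment (section 14.0). Photographs may be taken before later treatments and after treatment (sections 2.6 and 2.8), and biopsies on the treatment day (section 2.10).
- *That headache or fainting would be credited to the wrong device.* Section 2.14 lists these as occurring during treatment.
- *That the rank sum and t-tests would distort an outcome comparison.* Section 2.15.4 applies them to demographics and medical history only.

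**Conclusion.** The concern holds as a gap in design and attribution. The protocol permits dual-device subjects, asks for per-device results, and gives no rule on area, side, order or allocation. For dual-device subjects, 30- and 90-day satisfaction cannot be assigned to a device under any arrangement of areas. Follow-up photographs, biopsies and late local adverse events cannot be assigned if the area was shared. On the reading that every comparator user also has SoftWave, this touches all comparator follow-up data and k/50 of the SoftWave data, with k unknown.

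For pain, the documents give no size for the bias. Under an assumed 1-point order effect it runs from 0 with balanced order to 1 point with fixed order, in the within-subject contrast. Carry-over is a risk the design cannot exclude, not something the documents show to occur. The change should be made before the comparator is used.

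**What to change.** - Reconcile sections 2.1, 2.2, 2.3, 2.7 and 2.15.3 to 2.15.6. State whether the comparison is within-subject on separate areas or in separate groups, and whether the section 2.3 restriction covers the comparator.
- Where the comparator is used, take the assignment (side and order, or group) from a prepared random list, not from the operator.
- Record device and area with each pain score, local adverse event, photograph and biopsy. State in section 2.10 whether the contralateral control side is free of the comparator.
- In section 2.15, summarise area-level outcomes per device, with a within-subject comparison if subjects receive both. Show subject-level outcomes of dual-device subjects (satisfaction, late systemic adverse events) only in the overall table.

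Separate groups would also remove the attribution problem and would fit the wording of section 2.15. The choice is the sponsor's, but it must be stated.

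The cost is a short randomisation list, device and area fields on the forms, and revised analysis wording. Sites lose free choice of side and order, and per-device satisfaction tables become smaller. If every comparator user also has SoftWave, there will be no comparator satisfaction table.

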1.3 Duration of the Investigation

The sponsor anticipates that all subjects can be enrolled within 6 months. If subject participates in all required visits, then the subject's participation in this study may last up to 6 months. It is anticipated that it will take approximately 3 months to analyze the data collected during this study. The total duration of this study is anticipated to last approximately 15 months.

2.0 PROTOCOL

2.1 Protocol Methodology and Analysis

Methodology:

Subjects are to be enrolled in this clinical study if they are a healthy male or female 18 – 65 years of age. Up to 50 subjects will be enrolled at 2 study centers. Subjects will attend a screening/pretreatment visit which may be performed on the same day as the treatment visit. Subjects may receive up to 5 treatments with the study device. Subjects may also receive treatment

with a similar shockwave device. Subjects may be consented to have biopsies collected at a specific time after their final treatment, which will occur up to 30 days post treatment. Follow up visits may occur 30 and 90 days post last treatment visit. An unscheduled visit or phone call may be performed at any time during the study at the request of the subject or as deemed necessary by the site Investigator.

Analysis:

Upcoming generations are proving to have an interest in non-ablative aesthetic treatments and will drive demand for innovated products, procedures, and practice design.¹ Due to this shift in patient base, practices need to evolve to adapt to the newer generational ideologies. This device will be using the SoftWave device to collect additional data and imaging. Although this device is cleared for use by the U.S. Food and Drug Administration, there is a need to collect additional data, images, and tissue response to expand marketing claims.

Relevance:

There is an increasing demand for new methods and additional cleared indications for non-invasive treatments using shockwave therapy. Another device currently on the market cleared for use is, but are not limited to, the dermaPACE® System.

Testability:

The SoftWave device, had been previously cleared for the activation of connective tissue (FDA 510(k) K182682), the treatment of chronic, full thickness diabetic foot ulcers (FDA 510(k) K191961), and the treatment of superficial partial thickness second degree burns in adults (FDA 510(k) K200926). This study will utilize the collection of data and imaging to support additional marketing claims.

Compatibility:

Although shock wave technology is a well-known and widely use technique for non-invasive treatments, there is still a need to collect additional data and images, and expand marketing claims and device use.

Predictive power:

Assuming there is an acceptable side effect profile, it would be appropriate to expect results for other marketable indications.

2.2 Protocol Study Design

This is a prospective, open label, multi-center clinical study to collect additional data and imaging for the SoftWave device.

2.3 Subject Selection Criteria

Subjects will meet the criteria described below:

Inclusion Criteria:

- A healthy male or female 18 – 65 years of age.
- Willing to undergo treatments with the SoftWave device.

- Understands and accepts obligation not to receive any other procedures on the treatment area through the length of the study.
- Understands and accepts the obligation and is logically able to be present for all visits.
- Is willing to comply with all requirements of the study and sign the informed consent document.

Exclusion Criteria:

- Is pregnant or of childbearing potential and not using medically effective birth control, or has been pregnant in the last 3 months, currently breast feeding or planning a pregnancy during the study.
- The subject has a pacemaker or implantable defibrillator.
- The subject has a severe coagulation disorder.
- The subject has open epiphyseal plates.
- The subject has recently had a steroid injection.
- The subject is currently enrolled in an investigational drug or device trial, or has received an investigational drug or been treated with an investigational device within in the area to be treated 6 months to entering this study.
- The subject has any condition or is in a situation which, in the Investigator's opinion, may put the subject at significant risk, may confound study results or may interfere significantly with the subject's participation.

Be sure to list all concomitant medications taken or procedures performed before, during and after the trial.

Subjects will be recruited for the study through the existing patient database and may use advertisements.

Subject populations will not be eligible to participate in the study if they are vulnerable populations such as children, pregnant women, prisoners, institutionalized individuals, and any persons requiring a legally authorized representative as part of the consenting process.

Subject population characteristics that will not be eligible to participate in the study include non-English speaking individuals and people who cannot read or comprehend English. Employees of the Investigator will be participating in the study.

2.4 Screening

Subjects will be asked questions about their medical history, may have a limited physical and their inclusion/exclusion criteria will be verified. Discontinuation of any concomitant medications, specifically pain killers, may be discussed and post treatment instruction will be reviewed with the subject. Subjects will be informed of standard COVID-19 procedures that adhere to federal and state guidelines.

Procedure for the Limited Physical Exam:

If the investigator determines that a limited exam is necessary, the exam will be like a basic annual physical exam performed by a primary care doctor to determine general overall health. The limited

medical exam may include all or any of the following; vital signs such as blood pressure, heart rate, respiratory rate and body temperature, general appearance, listening to the heart, lungs and abdomen with a stethoscope, head and neck exam, in addition to examining the throat, tonsils, teeth, ears, eyes and nose as well as a neurological exam such as testing muscle strength, reflexes, balance, sensory changes of the extremities and mental state.

